8.4. Exclusion Criteria

- 1) Individuals with a diagnosis of an oropharynx, esophageal, or gastro-esophageal tumor, or ongoing symptoms of dysphagia.
- 2) Any history of esophageal varices, or active stricture.
- 3) Current use of anti-thrombotics (anti-coagulants and anti-platelet drugs) that cannot be safely discontinued for the appropriate drug-specific interval in the peri-administration period. Depending on the particular agent or reason for the anti-thrombotic therapy, it may not be necessary to discontinue anti-thrombotic agents. There could be circumstances where the drug may not need to be discontinued if the risk of bleeding is considered negligible (e.g. daily aspirin therapy). Physicians should use their clinical judgement and should consult relevant guidelines such as those provided by the ASGE.
- 4) Known bleeding disorder.
- 5) Individuals who have had a myocardial infarction or any cardiac event < 6 months prior to enrollment.
- 6) Individuals who have had a cerebrovascular event < 6 months prior to enrollment in which swallowing was affected.
- Prior ablative or resection therapy of the esophagus including radiofrequency ablation (RFA), photodynamic therapy (PDT), spray cryotherapy, endoscopic mucosal resection, and other ablation therapies.

- 8) Any history of esophageal surgery, except for uncomplicated fundoplication.
- 9) Do not need upper endoscopy as part of patient management.

10) Pregnancy

9. Study Procedures

9.1. Schedule of Events

Assessment	Screening/Enrollment Visit	Follow-Up Phone Call (7 days +/- 3 days after Enrollment)	Repeat Cytosponge
Informed Consent Form	х		
Demographics	X		
Medical History	X		
Inclusion/Exclusion Criteria	x		
Cytosponge Administration	x		\mathbf{X}^1
Visual Analog Scale	X ²		
Routine Care Endoscopy with Biopsy	X ^{3,4}		
Impact of Event Scale		X	
Procedure Preference and Acceptability Questionnaire		x	
Adverse Events ⁵	Х	X	Х

¹If the initial Cytosponge sample is inadequate, sites will be notified and subjects will be asked to return for repeat Cytosponge administration. Only the Cytosponge administration will be repeated. Questionnaires and the endoscopy procedure will not be repeated on these patients.

²VAS should be administered immediately following completion of the Cytosponge and prior to the upper endoscopy.

COVB2710467

Version G 01-DEC-2017

³Routine care biopsies should be taken during the endoscopy following the Cytosponge as this is considered standard of care for the target population.

⁴For subjects presenting for GERD, a single set of 4 quadrant biopsies (4 pieces of tissue total) of the gastric cardia (TGF+1) should be taken for this research study. The research specific biopsies will be taken in addition to any routine care biopsies taken during the procedure and will still be obtained even if routine care biopsies are not taken. The Sponsor will pay for any charges related to collection and pathology of the research specific gastric cardia biopsies.

It is encouraged for Investigators to take photos of the gastroesophageal junction (GEJ) during the endoscopy procedure.

⁵Every adverse event must be reported to the sponsor and recorded in the electronic case report form. Sites are responsible for following local IRB guidelines for reporting adverse events to their local IRB.

9.2. Subject Screening

During screening/enrollment, eligibility is assessed and those eligible and interested in participating are consented on the study. Once consent is obtained, subjects will undergo administration of the Cytosponge, complete a questionnaire, and proceed with routine care upper endoscopy immediately following completion of the Cytosponge in which biopsies are taken for clinical purposes and sent to pathology.

The following will be completed during the screening/enrollment visit:

- Eligibility review
- Informed consent
- Cytosponge administration
- Visual Analog Scale
- Routine care upper endoscopy with biopsy
- Adverse event assessment
- Enrollment case report form (CRF): This captures demographics including race, ethnicity, gender, and year of birth, relevant BE and GERD medical history including documentation of endoscopic procedures received to date as well as pathology findings and endoscopic history related to current diagnosis.

9.3. Visual Analog Scale Administration

Immediately following administration of the initial Cytosponge and retrieval, subjects will be administered a Visual Analog Scale (VAS). The VAS will not be administered during the repeat Cytosponge for subjects requiring a repeat Cytosponge.

This document is electronically controlled

COVB2710467

Version G 01-DEC-2017

9.4. Subject Consent

If a patient is screened eligible and interested in the study, the patient will be consented on the study prior to any study procedure. Written informed consent will be obtained by qualified study personnel. Documentation of the consent process will be maintained in the subject's research record.

Patients will be given ample time to review the consent document and ask any questions they may have. A copy of the written consent form will be provided to the subject and the original maintained in the subject's research record.

If patients meet all inclusion and none of the exclusion criteria and consent to the study, they will be enrolled in the study. Subjects will be assigned a unique subject code.

9.5. Cytosponge Abrasion Scale

Cytosponge abrasions will be carefully assessed during the endoscopy and graded using a standardized abrasion scale (see Appendix I: Cytosponge Abrasion Scale). Physicians performing the endoscopy will be trained on use of the scale.

9.6. Adverse Event Assessment

Subjects should be assessed for any adverse events occurring before, during, or after Cytosponge administration. All adverse events occurring during the research study must be reported to the sponsor. Sites are responsible for following local IRB guidelines for reporting adverse events to their local IRB.

9.7. Prior and Concomitant Medications

Current use of anti-thrombotics (anti-coagulants and anti-platelet drugs) including but not limited to warfarin, clopidogrel, heparin and/or low molecular weight heparinmay be discontinued as per discretion of the principal investigator. Reference Exclusion criteria #3.

9.8. Assessment of Safety

9.8.1 Methods and Timing of Assessing Safety Parameters

To monitor safety, subjects will be asked at each visit and during telephone contacts about changes in their medical conditions. Subjects will be able to contact the investigator at any time during the study if they note any change in their medical condition

Medtronic Confidential

9.8.2 Documenting Preexisting Conditions(s)

A preexisting condition is one that is present at the start of the study. A preexisting condition should be recorded as an adverse event if the frequency, intensity, or the character of the condition worsens during the study period.

9.8.3 General Physical Examination Findings

At screening, any clinically significant abnormality should be recorded as a preexisting condition. At the end of the study, any new clinically significant findings/abnormalities that meet the definition of an adverse event must also be recorded and documented as an adverse event.

9.9. Recording Data

Source data is all information, original records of clinical findings, observations, or other activities in a clinical trial necessary for the reconstruction and evaluation of the trial. Source data are contained in source documents. Examples of these original documents, and data records include: hospital records, clinical and office charts, laboratory notes, memoranda, subjects' diaries or evaluation checklists, pharmacy dispensing records, recorded data from automated instruments, copies or transcriptions certified after verification as being accurate and complete, microfiches, photographic negatives, microfilm or magnetic media, x-rays, subject files, and records kept at the pharmacy, at the laboratories, and at medico-technical departments involved in the clinical trial.

This study will utilize electronic case report forms (eCRFs). The study eCRF is the primary data collection instrument for the study. All data requested on the eCRF must be recorded. All missing data must be explained. If a space on the eCRF is left blank because the procedure was not done or the question was not asked, this should be documented in the comments field.

Along with the data collected during screening/enrollment, a follow-up phone call will be made and the following data will be collected:

- Impact of Event Scale
- Procedure Preference and Acceptability Questionnaire
- Adverse event assessment
- Follow-up electronic case report form (eCRF): This captures relevant information for questionnaire completion and assessment of adverse events.

9.9.1. Impact of Event Scale

The impact of event scale will be completed with the subject during the follow-up phone call and measures subjective distress related to administration of the Cytosponge. See **Appendix II:**

Impact of Event Scale.

COVB2710467

Page 29 of 61

9.9.2. Procedure Preference and Acceptability Questionnaire

The procedure preference and acceptability questionnaire will be completed with the subject during the follow-up phone call. This assessment collects subject preference for the Cytosponge or traditional upper endoscopy as well as willingness to undergo the procedure again.

9.9.3. Follow-up Phone Call Adverse Event Assessment

During the follow-up phone call, subjects should be assessed for any adverse events that have occurred since administration of the Cytosponge. Only those events potentially related to participation in this research study must be reported to the sponsor. Sites are responsible for following local IRB guidelines for reporting adverse events to their local IRB.

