11.1. Definitions/Classifications

Adverse event: any unwanted medical occurrence in a subject. An event is a sign, symptom, illness, abnormal laboratory value, or other medical event occurring to a subject that appears or worsens during a clinical study. Adverse events will be collected and documented after the subject has signed the

COVB2710467

Informed Consent form, until the completion of the final Cytosponge administration post-procedure 7-day phone call is completed; which will be considered to be the end of the study.

All adverse events will be graded as follows:

Mild: Sign or symptom, usually transient, requiring no special treatment and generally not interfering with usual activities.

Moderate: Sign or symptom, which may be ameliorated by simple therapeutic measures, may interfere with usual activity.

Severe: Sign or symptom that is intense or debilitating and that interferes with usual activities. Recovery is usually aided by therapeutic measures and the discontinuation of the study device may be required.

The relationship of the adverse event to the study is defined as follows:

No Relationship: An adverse event has no temporal relationship to study device or has a much more likely alternative etiology.

Possible: An adverse event has a minimal temporal relationship to the study device and/or a more likely alternative etiology exists.

Probable: An adverse event has a strong temporal relationship to study device, and an alternative etiology is unlikely or significantly less likely compared to the potential relationship to study device.

Definite: An adverse event was shown to be related to the study device.

Device Deficiency: Inadequacy of a medical device related to its identity, quality, durability, reliability, safety or performance such as a malfunction, misuse or use error or inadequate labeling.

Unknown: The relationship of the adverse event to the study device is inconclusive.

Adverse Event will be reported to Medtronic-GI Solutions utilizing the electronic case report (Adverse Event CRF eForm)

Adverse device effects: device related adverse events caused wholly or partly by the use of the device. A causal relationship between an observed adverse event and the use of the trial device may exist with various degrees of probability, on the basis of statistical probability, or of plausible medical data and considerations.

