In the case of adverse device effect with the Cytosponge[™] Cell Collection Device, the Cytosponge capsule should be postponed until adverse device effect is resolved and per physician discretion.

Serious adverse event is any adverse event that:

- Led to death
- Resulted in a life-threatening illness or injury
- > Led to persistent or significant disability or incapacity
- > Required inpatient hospitalization or prolongation of existing hospitalization
- > Led to fetal distress, fetal death, congenital anomaly/birth defect.
- Resulted in medical or surgical intervention to prevent life threatening illness or permanent impairment to body structure or body function.
- > Other significant medical event.

Some important medical events, although they may not result in death, be life-threatening, or require hospitalization may still be considered serious adverse events when, based upon appropriate medical

COVB2710467

judgment, they are felt to jeopardize the subject and may require medical or surgical intervention to prevent one of the outcomes listed above.

Life threatening means that the subject was, in the view of the investigator, at immediate risk of death from the reaction as it occurred. This does not include an adverse event that, if more severe, might have caused death.

Disability means a substantial disruption of a person's ability to conduct normal life's functions.

Serious Adverse Event will be reported to Medtronic-GI Solutions utilizing the electronic case report (Serious Adverse Event CRF eForm) within 24 hours of the investigator's awareness and reported to IRB within 10 working days.

An unanticipated adverse event is any serious, device related adverse event, if that event was not previously identified in the risk analysis and consent form in:

- a. nature
- b. severity or
- c. frequency
- d. Unreasonable risk is not defined. It shall be determined by management on a case-by case basis through evaluation of serious and unanticipated adverse events.

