11.2. Reporting of Adverse Events

It is the responsibility of the sponsor to notify all participating investigators of any adverse event associated with the study that is serious or unexpected.

Every adverse event should be recorded in the electronic case report form. Any safety or device deficiency issues which may occur during training with healthy volunteers shall be reported using the Field and Technical report (FTR, form-0021).

The following data must be documented:

- Type of event
- Subject number
- Time of occurrence: date, time
- Time of resolution: date, time
- Severity degree: mild / moderate / severe /
- Relationship to study device: no relationship/possible/probable/definite/unknown
- Measures taken
- Outcome of event: unchanged / worsened / improved / resolved / unknown / death

COVB2710467

Version G 01-DEC-2017

Page 34 of 61

If timely completion of the electronic CRF is not possible, a paper copy can be completed and sent via fax or email GI Solutions at Medtronic [contact] or [contact]. If for any reason the form cannot be completed within 24 hours, a phone call should be made to the sponsor to meet the reporting timeline. In the case of a telephone or faxed/emailed report, sites must still complete the electronic reportable event eCRF at the earliest possible opportunity, and no later than 72 hours following learning of the event.

All other reportable events should be reported within **15 days** of learning of the event. Any safety or device deficiency issues which may occur during training with healthy volunteers shall be reported using the Field and Technical report (FTR, form-0021).

12. Data Review Committees

Data Monitoring Committee (DMC) or Clinical Events Committee (CEC) will not be used for this study.

13. Statistical Design and Methods

For the primary objectives, to assess the acceptability of the Cytosponge in subjects with BE, we will assess the distribution of Impact of Event Scale scores, and the intrusiveness and avoidance subscales. We will generate measures of central tendency and distribution of these data. Bivariate analysis will be performed to assess for predictors of low tolerance of Cytosponge surveillance, and a logistic regression model created to assess these factors while controlling for potential confounders. Data will be compared to population norms in published literature¹ using parametric statistics. VAS scores will be calculated, and measures of central tendency and distribution reported.

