E	 Cardia Biopsies: For subjects presenting for GERD, a single set of 4 quadrant biopsies (4 pieces of tissue total) of the gastric cardia (TGF+3) will be collected during the endoscopy procedure. All research-specific gastric cardia biopsies, as well as any routine care tissue biopsies will undergo standard processing and H&E staining at the home institution, with assessment by expert gastrointestinal pathologists. The sponsor will pay for any charges related to collection and pathology of the research-specific gastric cardia biopsies. Removed from 3.1 General Design: "Biopsies not taken at the physician's 	Clinical Program Manager

COVB2710467

Version G 01-DEC-2017

Page 59 of 61

Medtronic

·		
•	discretion is not a protocol deviation." Photos of the gastroesophageal junction (GEJ): It is encouraged for investigators to take photos of the GEJ during the endoscopy procedure. Interim Analysis: In an effort to understand the sensitivity and specificity of the test, an interim analysis of the data, based on the statistical methodology outlined above, may be performed after approximately half the study subjects have primary outcomes. Quality Assurance of Cytosponge Samples: For quality assurance, Cytosponge samples may be sent to the University of Cambridge to be processed and read, as needed to optimize training at the central lab. These results will be compared to those reported by Miraca. Update to 3.5 Protocol Map : Map updated to include collection of gastric cardia biopsy in subjects presenting for GERD. Adverse Event (AE) Reporting Clarification: Updated wording from, "Only those events potentially related to participation in this research study" to "Every adverse event must be reported to the sponsor and recorded in the electronic case report form. See section 7.2 for definition of a reportable adverse event and documentation guidance." Removed "theoretical" and added "and/or irritation of" to section 7.2.4 Anticipated adverse events reactions associated with Cytosponge™ Cell Collection Device Updated Revision to Rev. E and Revision date to 15.December.2015	

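### Adverse events: Protocol 9.9.3 narrows what sites must report from the day-7 call, and no call is scheduled after a repeat Cytosponge although 11.1 presupposes one

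*Protocol*

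**What the plan says.** **Reporting scope.** Protocol 9.9.3 has sites ask at the follow-up call about any adverse event since the Cytosponge, then states: "Only those events potentially related to participation in this research study must be reported to the sponsor". Three other sections are wider:

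- 9.1, note 5: "Every adverse event must be reported to the sponsor and recorded in the electronic case report form". The note is attached to the adverse event row, which is marked for the follow-up call.
- 9.6: "All adverse events occurring during the research study must be reported to the sponsor".
- 11.2: "Every adverse event should be recorded in the electronic case report form". Its list of items to document includes "Relationship to study device: no relationship/possible/probable/definite/unknown", so unrelated events have a place on the form.

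**Follow-up after a repeat sponge.** Section 11.1 runs adverse event collection from consent to the 7-day call after the final Cytosponge, and treats that call as the end of the study. The sections that set the schedule provide less:

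- 9.1 has one call column, timed 7 +/- 3 days from enrolment. The repeat column is marked only for administration and adverse events, and note 1 says that nothing but the administration is repeated.
- 6.1 times the call from the Cytosponge and endoscopy procedures, puts participation at about 4 to 10 days, and ends it at the call.
- SAP 6.1.1 states that there is a single planned follow-up.

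Protocol version G gives no interval for the repeat. SAP 6.6.1.1.1 gives 30 +/- 10 days after the first administration.

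**The concern.** A site that follows only the section written for the call would withhold events it judges unrelated, and so would not meet 9.1 or 9.6. The site's judgement of relatedness then acts as a filter before the sponsor sees the event, and the filter may differ between sites.

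The repeat sponge raises a more serious problem. A subject with an inadequate first sample is exposed to the device twice but has scheduled follow-up after only one exposure. Safety is the fifth secondary objective, and its output is the number and percentage of subjects with Cytosponge-related adverse events (Protocol 13; SAP 6.6.1.1.7 and 6.7). A related event that appears some days after the second sponge belongs in that table, but no scheduled contact asks about it. The error can run only one way, towards under-counting.

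**Working it through.** No sample size or power figure is involved. The check compares the rules and does arithmetic on the visit windows.

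**1. Which events at the call must reach the sponsor?**

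| Section | Events covered | Duty |
|---|---|---|
| 9.9.3 | potentially related only | report to sponsor |
| 9.1 note 5 | every event | report to sponsor and record in eCRF |
| 9.6 | all events during the study | report to sponsor |
| 11.2 | every event | record in eCRF |

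The direct conflicts are with 9.1 note 5 and 9.6. Section 11.2 speaks of recording and conflicts only through 11.1, which makes the eCRF the reporting route: "Adverse Event will be reported to Medtronic-GI Solutions utilizing the electronic case report". Section 9.9.3 sets a minimum, so a site that reports everything complies with all four sections.

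What could be lost is narrow: non-serious events, judged unrelated and first disclosed at the call.

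- Serious events have their own 24-hour route in 11.1: "Serious Adverse Event will be reported to Medtronic-GI Solutions utilizing the electronic case report".
- The follow-up eCRF in 9.9 may still carry the rest: "This captures relevant information for questionnaire completion and assessment of adverse events".
- The Medical Monitor's remit covers serious, unanticipated and device-related events, not these.
- The planned tables count related events only.

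The part that can vary by site is the unrelated portion of the synopsis report of events by number, severity and relationship.

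**2. Can the single call serve a repeat sponge?** Days are counted from the first procedure, which is on the day of enrolment.

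- Call window: 7 - 3 = day 4 to 7 + 3 = day 10.
- Section 11.1 presupposes a 7-day call after the final sponge. Applying the same +/- 3 days (an assumption), that call comes at least 7 - 3 = 4 days after the repeat.
- Latest repeat day that leaves 4 days before the call: 10 - 4 = day 6 if the call is on day 10; 7 - 4 = day 3 if it is on day 7; 4 - 4 = day 0 if it is on day 4.
- By then the central pathologist must have read the sample, the site must have been notified and the subject must have returned.
- A repeat after day 10 has no later scheduled call.

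**3. The same check with the SAP's repeat interval.**

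- Repeat: 30 - 10 = day 20 to 30 + 10 = day 40.
- Time from the call to the repeat: 20 - 10 = 10 days at the shortest, 40 - 4 = 36 days at the longest.
- Call presupposed by 11.1: 20 + 4 = day 24 to 40 + 10 = day 50. No such call is scheduled.

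**4. Effect on the table.** With the full 275 subjects as denominator, each repeated subject whose only related event is missed lowers the reported percentage by 1/275 = 0.36 percentage points. The documents give neither a repeat rate nor a rate of delayed related events, so no total follows.

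**The case against.** The strongest reply is that the gap is one of wording. Section 11.1 refers to the final administration, which has meaning only if a repeat is possible, and a site that followed 11.1 would call again. Section 6 and the SAP summary time the call from Cytosponge administration, which can be read to include a repeat. Note 1 to the 9.1 schedule is not literally exhaustive, since adverse events are marked in the repeat column. That questionnaires are not repeated does not rule out a call about adverse events alone.

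Much of this stands as a reading of 11.1, but it does not supply the call. The schedule that sites work from has no such column, and SAP 6.1.1 counts one follow-up. The call described in section 6 also completes a questionnaire that is not given again, and 6.1 ties the call partly to an endoscopy that is not repeated. Section 9.8.1 lets subjects contact the investigator during the study, but that is passive, and 6.1 treats participation as complete once the follow-up call is done.

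Four limits are accepted:

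- The conflict over 9.9.3 is minor on its own.
- Events at the repeat visit itself are collected.
- The day 20 to 40 figures rest on the SAP alone.
- The number of subjects affected is unknown, and the study is a descriptive pilot.

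**Conclusion.** Both parts hold on the current text. The reporting conflict is clear but has little effect: it cannot change the related-event tables, and touches only unrelated, non-serious events first heard of at the call. The missing call after a repeat carries the weight. For a repeat after day 10, scheduled contact after the repeat visit is zero. That conclusion does not use the SAP interval, which only shows that the gap would be the normal case: every repeat from day 20 to day 40 falls after the call window has closed.

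The possible bias is towards fewer related events among subjects exposed twice. Its size cannot be stated from the documents. The conclusion assumes that sites follow the 9.1 schedule and 6.1 rather than infer a further call from 11.1. The point should be fixed. It is not a threat to the study's main conclusions.

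**What to change.** 1. In Protocol 9.9.3, replace the limiting sentence with the rule in 9.1 and 9.6: all adverse events learned at the call go to the sponsor, and relatedness is recorded in the field that 11.2 already provides.
2. In Protocol 9.1, add a call 7 (+/- 3) days after any repeat sponge, for adverse events only, and name it in note 1 as the one further element that is repeated.
3. Align Protocol 6.1 (length and end of participation) and SAP 6.1.1 (number of planned follow-ups) with 11.1. Section 9.11 can stand, since it ties completion to the last study visit.

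The cost is one replaced sentence, wording changes in three other places, the sponsor and IRB approval that Protocol 15.6 requires, and one phone call per repeated subject. No new data field is needed.

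A related point for the sponsor: 7.2 relies on the endoscopy that follows the sponge to deal with detachment or bleeding, and 10.1 relies on it for detachment. A repeat is given without endoscopy, so the protocol should say how these events are handled then.
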